2.2 Trial Design

This trial is a Phase 2, multicenter, double-blind, randomized, placebo-controlled, parallel-group trial to assess the efficacy and safety of daxdilimab in patients with active, proliferative lupus nephritis despite standard of care.

Approximately 210 participants will be randomized in a ratio of 1:1:1 (70 participants per group) to receive either daxdilimab [redacted] mg or [redacted] mg SC or placebo SC in addition to SOC background therapy as described below in [Table 2](#). Randomization will be stratified by:

- Pre-randomization urine protein to creatinine ratio (UPCR) < 3.0 mg/mg vs. \geq 3.0 mg/mg
- Screening eGFR < 60 mL/min/1.73m² vs. \geq 60 mL/min/1.73m²

Table 2 Stage I Treatment Assignment

[figure not shown]

[figure not shown]

Table 3 Stage II Treatment Assignment

A large rectangular area of the page has been completely blacked out, obscuring the content of Table 3.

The basic study flow diagram is presented in [Figure 1](#)

Figure 1 Study Flow Diagram

CRR = complete renal response; D = day; IP = investigational product; MMF = mycophenolate mofetil; MPA = mycophenolic acid; OCS = oral corticosteroids; PRR = partial renal response; [REDACTED] SC = subcutaneously; SFU = Safety Follow-Up; SOC = standard-of-care; W = week.

2.3 Sample Size

A sample size of approximately 210 participants (up to approximately 70 participants per treatment group) is planned for this trial. The sample size was calculated based on the primary efficacy endpoint. Assuming a placebo response rate of 25%, 70 participants per treatment group will provide approximately 80% power to detect an increase in response of 20% in either arm of a daxdilimab group as compared to the placebo group at the 2-sided alpha level of 0.10 using a Chi-square test. The minimum detectable difference is 13% between the daxdilimab group and placebo group. The assumption of 25% responder rate for placebo is based upon published results ([Mejia-Vilet et al., 2021](#)).

3 PLANNED ANALYSES

[REDACTED]

[REDACTED]

[REDACTED]

[REDACTED]

3.2 Planned Primary Analysis

The primary analysis will be conducted after the last participant has completed the Week 52 Visit or discontinued from study early. For the primary analysis, all the efficacy and safety data collected prior to the data cut-off will be analyzed.

3.3 Planned Final Analysis

The final analysis will be conducted after all participants have completed Week 112 Visit or discontinued early from the study.

4 STATISTICAL METHODS

4.1 General Considerations for Data Analyses

All statistical calculations will be primarily performed using SAS® System Version 9.4 or higher (SAS Institute Inc., Cary, NC, USA).

The primary comparison will be between the daxdilimab [REDACTED] mg or [REDACTED] mg group and the placebo group. For primary and second efficacy analyses, the data up to the [REDACTED] Visit will be used. The applied methods for statistical descriptive analysis and presentations will be based on the types of variables being tested.

- 1) Overall summary of descriptive statistics for continuous variables will include, not limited to, the number of observations, mean, standard deviation, median, minimum, and maximum, first quartile, and third quartile values in each treatment group
- 2) Overall summary of descriptive statistics for categorical variables will include, not limited to, frequency counts, percentage of patients or point estimate

Data summaries for Stage I of the Treatment Period will be presented by randomized treatment group (i.e., “daxdilimab [REDACTED] mg”, “daxdilimab [REDACTED] mg” and “Placebo”) and overall. Data summaries for Treatment Period Stage II (i.e., the Stage II period beginning at the [REDACTED] Visit) will be presented according to the reassigned treatment regimen with respect to achievement of PRR (or CRR) at Weeks 48 and maintained through Week 52 (e.g., “daxdilimab [REDACTED] mg [REDACTED] mg [REDACTED]”, “daxdilimab [REDACTED] mg [REDACTED] mg [REDACTED]”, “Placebo [REDACTED]/Placebo [REDACTED]”, and “Placebo [REDACTED]/daxdilimab [REDACTED] mg [REDACTED]”). For the longitudinal analysis covering two-stage periods (Stage I and Stage II) of treatment, participants will be analyzed according to the combination of treatment that they actually received in Stage I and Stage II treatment period.

Summaries of study and participant characteristics (e.g., demographics and baseline characteristics, medical history, protocol deviations) will be reported.

For additional details on data presentation, refer to the Statistical Programming Plan (SPP).

Table 4 provides the overview of the study periods for reporting purposes. All major analysis endpoints will be reported for Stage I and Stage II. All assessments, unless otherwise specified, will be included in by-patient listings. Data collected at unscheduled visits may be used in the data analysis and will not be presented in the summary statistics report.

Table 4 Study Periods

Study Period	Description
Stage I	Day 1 to [REDACTED] trial intervention administration and safety/efficacy assessments
Stage II	Post [REDACTED] trial intervention administration and safety/efficacy assessments + safety follow-up

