4.4 Analysis Sets

4.4.1 Full Analysis Set

The Full Analysis Set will include all randomized participants who receive any dose of trial intervention in the study. Participants will be analyzed according to the treatment randomized. The efficacy analysis will be based on the Full Analysis Set.

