4.15 Final Analysis

The final analysis will be conducted after all participants have completed the Week 112 Visit or discontinued early from the study.

By study design, the participants may undergo the different [REDACTED] based upon the renal response observed at Week 48 and Week 52. Thus, in the final analysis, the participants will be divided into two subgroups based on their PRR/CRR status at the Week 48 through Week 52:

- PRR/CRR Subgroup: Participants who achieved PRR or CRR at Week 48 and sustained through Week 52 will remain in their treatment groups. Statistical modeling can be used to examine the treatment effect between treatment groups over the Stage II of treatment (i.e., [REDACTED] mg [REDACTED] vs. placebo and [REDACTED] mg [REDACTED] vs. placebo), as applicable. All endpoints defined in primary, secondary and [REDACTED] will be analyzed. Some key endpoints examples are highlighted below.
- Non-PRR/CRR Subgroup: Participants who did not achieve PRR or CRR at either [REDACTED] will be administered daxdilimab [REDACTED] mg SC [REDACTED] through [REDACTED] (last dose administered at [REDACTED]). The final analysis for this subgroup will be descriptive only. No statistical modeling will be performed and no formal statistical comparison between treatment groups will be tested. All endpoints defined in primary, secondary and [REDACTED] except for all time-to-event endpoints, will be analyzed. Some key endpoints examples are highlighted below.

In the final analysis, all analyses planned for the primary analysis will be rerun with the Full Analysis Set.

For the non-PRR/CRR subgroup, the following analyses up to the Week 112 visit will be covered in the final analysis using Stage II Analysis Set:

- Proportion of participants achieving PRR or CRR or [REDACTED] in the Stage II
- Change from baseline in eGFR. In addition, change from re-baseline (Week 64) in eGFR will be explored descriptively
- Change from baseline in UPCR. In addition, change from re-baseline (Week 64) in UPCR will be explored descriptively

- Proportion of participants with prednisone-equivalent dose ≤ 2.5 mg/day for participants with baseline OCS > 2.5 mg/day until Week 92

■ [REDACTED]
■ [REDACTED]
■ [REDACTED]

For the PRR/CRR subgroup, the following analyses using the data up to the Week 112 visit will be covered in the final analysis using Stage II Analysis Set:

- Proportion of participants sustaining PRR or CRR or [REDACTED] in the Stage II

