- Time to loss PRR or CRR in the Stage II after achieving PRR/CRR at Week 48 and Week 52
- eGFR slope
- Change from baseline in UPCR
- Proportion of participants with prednisone-equivalent dose ≤ 2.5 mg/day for participants with baseline OCS > 2.5 mg/day until Week 104
- [REDACTED]
■ [REDACTED]

In the final safety analysis, the data up to the Week 112 visit (see Section 4.9) will be used.

Summary statistics will be computed and displayed by treatment group for the PRR/CRR subgroup or by treatment pathway ([REDACTED] mg \rightarrow [REDACTED] mg, [REDACTED] mg \rightarrow [REDACTED] mg, placebo \rightarrow [REDACTED] mg) for the non-PRR/CRR subgroup and by visit, where applicable. Descriptive statistics for continuous variables will minimally include the number of participants, mean of the observed values/change from baseline, SD, minimum, median, and maximum. For categorical variables, frequencies and percentages will be presented. For analyses involved with statistical modeling, the analysis methods are as follows (if applicable):

- Time to loss at least PRR status: Kaplan-Meier cumulative distribution curves will be generated for each treatment group. Participants will be censored at the earliest of their treatment discontinuation time, receipt of rescue therapy, study withdrawal or death or at Week 112 when the event of at least PRR cannot be sustained after Week 52. A corresponding summary table will present the number of participants at risk, the number of participants responding, and the number of participants censored at each postbaseline time point by treatment groups. The table will also present the median, along with the corresponding 2-sided 90% CI of time to response. Cox proportional hazards model will be explored (if applicable) with treatment group included in the model adjusting for eGFR and 24-hour UPCR values collected at Week 52. The hazard ratio with associated 2-sided 90% CIs and p-values will be presented
- For continuous and binary endpoint endpoints, similar analysis methods will be applied as described in Section 4.8.3.2 of the SAP
- [REDACTED]
■ [REDACTED]

A line plot of proportion of PRR, CRR, [REDACTED] over time will also be produced by randomized treatment group or treatment pathway within each of the subgroups. Boxplots of change of [REDACTED] will also be plotted by randomized treatment group or treatment pathway within each of the subgroups.

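### SAP 4.1 groups two-stage longitudinal analyses by treatment received, which sorts placebo participants by their own Week 48–52 response; no readable analysis over both stages keeps the randomised arms whole

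*SAP*

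**What the plan says.** SAP 4.1 sets three grouping rules.

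- Stage I: "Data summaries for Stage I of the Treatment Period will be presented by randomized treatment group".
- Stage II: summaries are given "according to the reassigned treatment regimen with respect to achievement of PRR (or CRR) at Weeks 48 and maintained through Week 52". The examples listed include Placebo/Placebo and Placebo/daxdilimab as separate groups.
- Both stages together: "participants will be analyzed according to the combination of treatment that they actually received in Stage I and Stage II treatment period".

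SAP 4.15 shows what determines the Stage II regimen. It is chosen "based upon the renal response observed at Week 48 and Week 52". On responders it says: "Participants who achieved PRR or CRR at Week 48 and sustained through Week 52 will remain in their treatment groups". The other group is introduced as "Non-PRR/CRR Subgroup: Participants who did not achieve PRR or CRR at either" (the visits are blacked out), and all of it receives daxdilimab at a single blacked-out dose. Line plots of response over time are drawn "by randomized treatment group or treatment pathway within each of the subgroups".

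For the Full Analysis Set (FAS), which is the efficacy population, SAP 4.4.1 says: "Participants will be analyzed according to the treatment randomized". The primary and secondary analyses (SAP 4.8.1.2 and 4.8.2.2) use that set.

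**The concern.** The Stage II part of a treatment combination is a consequence of the outcome under study. Grouping by it conditions on a post-randomisation response, so the groups are no longer the ones that randomisation made comparable. Because the rule covers both stages, it also labels Stage I visits by a response seen only at Weeks 48 to 52. The placebo curve would divide into a good one and a poor one during the first year, when all of these participants were on the same treatment.

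A combination also requires a Stage II dose, and SAP 4.9.2.3 and 4.15 place the start of Stage II dosing at Week 64. A participant who never reaches it has no combination, and the SAP does not say where that participant is shown.

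At stake is the reading of the two-year curves. A gap between Placebo/Placebo and a daxdilimab group could be taken as evidence for or against a lasting drug effect when part or all of it is selection.

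**Working it through.** **1. The plan's own figure.** SAP 2.3 gives 70 per arm, CRR of 25% on placebo and 20 points more on daxdilimab (45%), two-sided alpha 0.10, and power of about 80%. With pooled rate 0.35:

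- Standard error under the null: √(2 × 0.35 × 0.65 / 70) = 0.0806
- Standard error under the alternative: √((0.25 × 0.75 + 0.45 × 0.55) / 70) = 0.0788
- Power = Φ((0.20 − 1.645 × 0.0806) / 0.0788) = 0.804

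This reproduces. It supplies the 25% and 45% used below. The documents give no rate for PRR or better.

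**2. Who is in each group.**

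| Randomised to | PRR/CRR at Week 48, sustained through Week 52 | Stage II | Combination |
|---|---|---|---|
| Placebo | yes | placebo | Placebo/Placebo |
| Placebo | no | daxdilimab | Placebo/daxdilimab |
| Either daxdilimab arm | yes | own group's regimen | own group |
| Either daxdilimab arm | no | one daxdilimab dose | same or different; dose blacked out |

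If assignment follows the rule, the sustained response is 100% in Placebo/Placebo and 0% in Placebo/daxdilimab.

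**3. Sizes of the two placebo groups.** Assume that a share p = 25% to 60% of placebo has a sustained response of PRR or better. The lower end is the plan's CRR rate, which p cannot be below; the upper end is an assumption. The 70 placebo participants then divide into about 18 and 52 (p = 25%) up to 42 and 28 (p = 60%).

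**4. Carry-over to another outcome when the drug does nothing.** Let response be a cut at z on a standard normal score. Let a later outcome correlate with that score at ρ = 0.3 to 0.7 (assumed). With φ the normal density, in SD units:

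- Placebo/Placebo minus Placebo/daxdilimab = ρφ(z) / [p(1 − p)]. For p = 25%, φ(z) = 0.318, giving 0.51 (ρ = 0.3) to 1.19 (ρ = 0.7). Over the whole range it is about 0.5 to 1.2 SD.
- Placebo/Placebo minus a daxdilimab arm left whole = ρφ(z) / p, or 0.19 to 0.89 SD.
- Both arms cut to responders, with response of 25% against 45% and a later outcome that depends only on underlying prognosis: ρ × (0.880 − 1.271), so daxdilimab responders look worse by 0.12 to 0.27 SD.
- Grouped as randomised: expected difference 0. In 5,000 simulated trials per setting, a nominal 0.10 test rejected in 8.5% to 10.4% of trials.

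**5. Why the size for CRR cannot be settled.** Take the plan's 25% against 45%. Assume placebo PRR-or-better of 40% to 50%, with all complete responders dosed in Stage II. Placebo/Placebo then shows CRR of 25/40 = 62.5% to 25/50 = 50%. Against this:

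- Daxdilimab arm whole, nobody lost: 45%, a difference of −17.5 to −5 points.
- Daxdilimab arm whole, 15% undosed and left out: 45/85 = 53%, a difference of about −10 to +3.
- Daxdilimab arm also cut to responders, with PRR-or-better of 60% to 70%: 45/60 = 75% or 45/70 = 64%, a difference of about +12 to +14.

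The randomised contrast is +20 in every case. The displayed figure depends on inputs that the documents do not give.

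**The case against.** The strongest reply is that SAP 4.1 is general text and SAP 4.15 governs the two-year analysis. That section sets responders against responders, makes the non-responder subgroup descriptive only, and draws its line plots within subgroups. Placebo responders against an undivided daxdilimab arm is not a contrast that the readable text plans. The first-year contrast also stays visible: Stage I summaries and the primary and secondary analyses are by randomised group, and SAP 4.15 reruns the primary-analysis outputs on the FAS.

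Much of this stands. It does not remove the point, for three reasons.

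- The 4.15 subgroups are themselves defined by a post-randomisation response, and that section allows modelling of treatment effect among responders. As the third result in step 4 shows, comparing responders with responders is not a randomised comparison.
- The rerun repeats the Week 52 analyses. The last visit of the longitudinal CRR presentation in SAP 4.8.1.2 is blacked out, so it cannot be counted as a two-stage display by arm.
- SAP 4.1 states its rule for two-stage analyses without reference to 4.15 and without calling the result descriptive.

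A reader might infer that participants not dosed in Stage II are dropped. The SAP does not say so: Table 5 keeps them in the Stage I safety summary, and the FAS rerun keeps them too. The gap is that the 4.1 rule gives them no group.

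**Conclusion.** The point holds for analyses spanning both stages. The placebo arm is certainly divided by response. The division of the daxdilimab arms is unknown, because 4.15 names two daxdilimab responder groups and one non-responder dose, all blacked out. No readable two-stage analysis keeps the three arms whole. The 100% and 0% follow from the design; every SD shift and CRR difference above rests on assumed PRR rates, correlations or undosed shares.

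Four stronger readings are tempting and are not supported.

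- That the Week 52 result is compromised. It is not: the primary and secondary comparisons and the fixed-sequence test stay as randomised.
- That a 20-point advantage would vanish or reverse. This needs an undivided daxdilimab arm and assumed PRR rates; with both arms cut to responders the sign does not change.
- That nobody in Placebo/daxdilimab has PRR at Week 52. Someone who missed it at Week 48 and met it at Week 52 has no sustained response, so only the sustained response is 0%.
- That these curves are the trial's main evidence on durability. Redaction hides which endpoints fall under the rule and whether tests are attached.

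This should be changed before the two-year figures are programmed. It does not threaten the primary analysis.

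**What to change.** Replace the two-stage sentence in SAP 4.1 with wording to this effect:

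- Efficacy analyses covering both stages are presented by randomised arm on the FAS, including participants not dosed in Stage II. They are read as the effect of initial assignment plus the response-based Stage II rule.
- Stage I visits are not grouped by Stage II treatment.
- Treatment-combination displays, and the response-subgroup displays and models of 4.15, may be kept. They are labelled descriptive and are not read as randomised comparisons.

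The text should also say how participants not dosed in Stage II are handled after Week 52. Protocol 4.1 requires scheduled visits only to Week 52 for those who stop dosing before then, so their later UPCR and eGFR values may be missing.

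The cost is SAP wording and a few extra figure shells, with no new data. The downside is that the Stage II placebo curve mixes participants still on placebo with those moved to daxdilimab. It cannot show the effect of continued daxdilimab against continued placebo, and a footnote should say so.

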4.1.1 Definition of Baseline

Unless otherwise specified, baseline is defined as the last non-missing valid observation prior to the first dose of trial intervention. In cases where baseline measurements are taken on the same day as trial intervention and no times are reported, it will be assumed that these measurements are taken prior to trial intervention being administered.

At [REDACTED] participants from all three Treatment Groups will be assigned to a [REDACTED] [REDACTED] based upon the renal response observed at [REDACTED] [REDACTED]. All participants who did not achieve the primary endpoint will be re-baselined at [REDACTED]. A re-baseline is defined as the last available assessment prior to the first quarterly dose of study intervention administered at [REDACTED].

4.1.2 Analysis Windows

Analysis visit windows will be used for all visit-based assessments to map longitudinal observations to scheduled visits and thereby allow for by-visit analyses, since not all assessments are performed on the scheduled day. Unless otherwise specified, all longitudinal efficacy, safety, and [REDACTED] will be based on the analysis visit windows. The analysis visit windows will be calculated by bisecting the interval between adjacent scheduled visit days except for the first post-treatment visit and the [REDACTED] visit. The first post-treatment visit will start at Day 2. When mapping to the [REDACTED] analysis window, this should only occur for assessments on or before the date of the nominal [REDACTED] dosing. Assessments after this date will be mapped to the following analysis visit windows. The detailed analysis visit windows will be specified in the SPP. The actual assessment day will be mapped to the windows defined for each scheduled study visit by the following rules:

- If more than one assessment falls within a visit window, the closest non-missing assessment to the scheduled day will be used in the analysis.
- If 2 non-missing assessment actual dates are equidistant from the target day, the later visit will be used in the analysis.
- For retest values of laboratory data, the retest value will be chosen.

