Participants who prematurely stop dosing prior to Week 52 will be followed for regularly scheduled visits through Week 52 unless participants withdraw consent of trial participation (See Section 7.1.3) or are lost to follow-up (See Section 7.2). Participants should be followed to assess AE/SAEs for at least 12 weeks after the last study intervention administration, approximately 4, 8, and 12 weeks after the last study intervention dose, unless the participant withdraws consent.

Participants who prematurely stop dosing after Week 52 but remain in the study will be complete the EOT Visit and the SFU Period, unless the participant withdraws consent. Participants will not automatically be removed from the trial if any administration of study intervention is missed.

Early discontinuation of study intervention for reasons other than lack of efficacy

An individual participant will not receive any further study intervention if any of the following occur in the participant:

- Receipt of Prohibited Medications (See Section 6.7.2).
- A Common Terminology for Adverse Events (CTCAE v5.0 dated 27 NOV 2017) Grade 3 or higher allergic reaction to the study intervention.
- A CTCAE Grade 3 or higher infection considered related to the study intervention.
- Other AE that contraindicates further dosing in the opinion of the Investigator and/or the Sponsor, or Medical Monitor.

- Withdrawal of consent from further treatment with study intervention.
- Participant is determined to have met one or more of the exclusion criteria or failed to meet all the inclusion criteria for study participation and there is a potential safety risk associated with continuation identified upon consultation with the Medical Monitor.
- Pregnancy or a decision to become pregnant.
- Any of the following liver function abnormalities:
 - alanine aminotransferase (ALT) or aspartate aminotransferase (AST) $\geq 8 \times$ ULN.
 - ALT or AST $\geq 5 \times$ ULN for more than 2 weeks.
 - ALT or AST $\geq 3 \times$ ULN and total bilirubin $\geq 2 \times$ ULN.
 - ALT or AST $\geq 3 \times$ ULN with the appearance of fatigue, nausea, vomiting, right upper quadrant pain or tenderness, fever, rash, and/or eosinophilia ($\geq 5\%$).

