4.9.2 Additional Safety Assessment

4.9.2.1 Clinical laboratory Evaluations

Laboratory assessments are defined in Section 8.2.4 of Protocol. All protocol-required laboratory tests must be conducted in accordance with the laboratory manual and the Schedule of Activities (SoA). Any clinically significant value will be reported as an AE. The laboratory results must be retained with source documents.

Clinical laboratory evaluations will be summarized for each treatment group and overall. The summary of clinical laboratory data will be generated for the Stage I data based on the Safety Analysis Set, and for the Stage II data based on Stage II Analysis Set. For analysis purposes, laboratory results based upon standardized units will be used. All data will be presented in listings, and a specific listing of abnormal results will be provided.

The following summary will be provided for hematology and biochemistry and lipid profile by treatment groups:

- Observed values and changes from the baseline by visit
- Worst toxicity grade
- At least 2-grade shift from baseline to worst toxicity
- Shift from the baseline relative to the normal range

In addition, the number and percentage of participants with the following liver-related abnormalities will be summarized if the following criteria is met at any post-baseline visit:

- AST or ALT: (a) $\geq 3 \times$ ULN; (b) $\geq 5 \times$ ULN; (c) $\geq 8 \times$ ULN
- Total bilirubin: $\geq 2 \times$ ULN

- ALT or AST $\geq 3 \times$ ULN and total Bilirubin $\geq 2 \times$ ULN
- ALT or AST $\geq 5 \times$ ULN for more than 2 weeks

The following summary will be provided for urinalysis by treatment groups:

- Observed values and changes from the baseline by visit
- Shift from the baseline relative to the normal range

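### The SAP's retest, closest-value and unscheduled-data rules do not exempt the worst-grade and liver-threshold tables, so a true laboratory peak can be missing from them

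*SAP*

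**What the plan says.** SAP 4.1.2 sets the scope of the visit windows with the words "Unless otherwise specified, all longitudinal efficacy, safety, and", followed by a redacted item. Safety data are therefore covered by default. Two of its selection rules matter here:

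- "If more than one assessment falls within a visit window, the closest non-missing assessment to the scheduled day will be used in the analysis"
- "For retest values of laboratory data, the retest value will be chosen"

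The retest rule does not require that the original sample was invalid. The detailed windows are left to the Statistical Programming Plan.

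SAP 4.1 adds: "Data collected at unscheduled visits may be used in the data analysis and will not be presented in the summary statistics report".

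SAP 4.9.2.1 plans, for hematology, biochemistry and lipids, the worst toxicity grade and "At least 2-grade shift from baseline to worst toxicity". For the liver it counts participants "if the following criteria is met at any post-baseline visit". The rows are ALT or AST at 3, 5 and 8 x ULN or more, bilirubin at 2 x ULN or more, the two combined, and ALT or AST at 5 x ULN or more for over two weeks. The section does not say whether these tables draw on all values or only on the windowed ones. It does send all laboratory data to listings, with a separate listing of abnormal results, and has clinically significant values reported as adverse events.

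Protocol 7.1.1 ends study intervention for "Any of the following liver function abnormalities". Three of its four liver criteria have a matching row in SAP 4.9.2.1: 8 x ULN, 5 x ULN for over two weeks, and 3 x ULN with raised bilirubin.

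**The concern.** Choosing one representative value per visit suits means and changes by visit. It does not suit a maximum or a duration. A worst-grade or threshold table asks whether a level was ever reached, and a rule that prefers the value nearest the target day, or the later repeat, can discard the result that answers the question.

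Protocol section 8 says that repeat or unscheduled samples may be drawn for safety reasons as well as for technical faults. When the reason is safety, the original may be the signal. A participant could then be stopped on an observed liver value and yet be absent from the SAP row for the same criterion. Safety is a stated objective of the trial, and these are the tables in which a numerical imbalance against placebo would be read.

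**Working it through.** The documents give no figure to reproduce. The check applies the written rules to hypothetical ALT series.

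**Schedule.** The week row of the activity tables is redacted. The weeks are inferred from the visit count, the unredacted week lists in Protocol 8.1 and 8.4, and the list of second-year telehealth weeks. Chemistry is marked at every first-year treatment visit (4-weekly from Week 4). In the second year it falls at Weeks 64, 76, 88, 100, 104 and 112.

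**Windows.** Target day = 7 x week + 1, with boundaries at the midpoints between adjacent visits.

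- Week 16 (day 113) lies between day 85 and day 141. Midpoints are (85 + 113)/2 = 99 and (113 + 141)/2 = 127, so the window is days 100 to 127, or 28 days.
- Week 76 (day 533) lies between day 449 and day 617. Midpoints are (449 + 533)/2 = 491 and (533 + 617)/2 = 575, so the window is days 492 to 575, or 84 days. This assumes that only laboratory visits define the chemistry windows.

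**Three hypothetical series (ALT as a multiple of ULN).**

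| Series | Values | Maximum, all values | Maximum, SAP rules |
|---|---|---|---|
| A | Day 85: 1.1; day 113: 8.6; retest day 118: 2.4; day 141: 1.2 | 8.6 | 2.4 |
| B | Day 449: 1.0; unscheduled day 510: 6.2; day 533: 1.3 | 6.2 | 1.3 |
| C | Day 85: 1.1; day 113: 1.2; unscheduled days 122 and 125: 5.5 and 6.0; day 141: 1.4 | 6.0 | 1.4 |

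- In A, days 113 and 118 share the Week 16 window and the retest replaces the original. The participant leaves the 3, 5 and 8 x ULN rows, although 8.6 meets the 8 x ULN criterion in Protocol 7.1.1. The loss comes from the retest rule alone: the closest-value rule would have kept day 113. If the retest were itself treated as unscheduled and excluded, the original would stand. The SAP does not say which rule takes precedence.
- In C, the peak is lost if unscheduled data are excluded. It is also lost if they are admitted, because the scheduled value is 0 days from target and the unscheduled ones are 9 and 12 days away.
- B behaves like C under the 84-day window. If the telehealth visits also define windows, Week 72 (day 505) covers days 492 to 519, since (477 + 505)/2 = 491 and (505 + 533)/2 = 519. Day 510 then falls in a window with no scheduled chemistry and counts only if unscheduled data are admitted.

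**Duration row.** Two consecutive scheduled values 28 days apart can show an elevation of more than 14 days, so first-year visits can support this row. An elevation that lasts over two weeks but resolves before the next 4-weekly or 12-weekly sample cannot be confirmed without unscheduled values.

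**The case against.** The strongest reply concerns scope. SAP 4.1.2 says that the windows exist to allow by-visit analyses, and SAP 4.9.2.1 lists its by-visit summaries separately from worst grade and shift. The liver rows count any post-baseline visit. SAP 4.1 allows unscheduled data into the analysis, and SAP 4.8.1.7.1 uses an unscheduled 24-hour UPCR in the primary endpoint, so there is no general ban. The programming plan, which is not available here, may settle the matter. This benign reading is tenable. It is not stated, however, and the default scope in 4.1.2 points the other way. The two readings give different counts.

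The second reply is that the cases are not lost to the report. Listings hold every value. SAP 4.9.1 tabulates Grade 3 or higher events and events leading to discontinuation, and SAP 4.5 summarises the reasons for stopping treatment. This stands, and it limits the harm. Listings, however, give no comparison between arms. Adverse event entry depends on the investigator's judgement of clinical significance, and Protocol 8.3.3 prefers the diagnosis over the abnormal test. Neither replaces a numerical threshold table.

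A reader might infer that only abnormal values are retested, so that the arm with more toxicity loses most. The documents do not support that: Protocol section 8 also allows technical repeats, for which preferring the retest is right.

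**Conclusion.** The point holds as a risk in the text as written, and it should be fixed. Under a literal reading, SAP 4.1 and 4.1.2 can remove a true peak from the worst-grade, shift-to-worst and liver-threshold tables, including for a participant stopped under the matching criterion in Protocol 7.1.1. The three series show that this can happen. They are invented and say nothing about how often.

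The size cannot be estimated: the documents give no rate of retesting, no rate of unscheduled sampling and no course of enzyme recovery. An elevation that persists at the next scheduled visit would still be counted. A reader might go further and conclude that the laboratory safety result is biased toward no toxicity. The documents do not support that, because the benign reading is open and because the listings, adverse event and disposition outputs remain. No formal safety hypothesis is planned (SAP 4.9.1). Neither liver injury nor cytopenia is among the potential risks named in Protocol 2.2.1.

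**What to change.** - **SAP 4.1.2:** limit the closest-value and retest rules to by-visit summaries.
- **SAP 4.9.2.1:** state that worst toxicity grade, shift to worst and all liver-threshold rows use every valid post-baseline laboratory value in the period: scheduled, unscheduled, original and retest. Leave out an original only when the sample is documented as technically invalid.
- **SAP 4.9.2.1:** evaluate the row for ALT or AST at 5 x ULN or more for over two weeks on actual sample dates.
- **SAP 4.1:** amend the sentence on unscheduled data to agree. For example, say that such visits get no row of their own in by-visit tables but do enter worst-case summaries.

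The cost is a few sentences and a programming flag, with no new data. The downside is that some reported toxicity percentages will be higher.
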